3.2 Current Knowledge of Ketogenic Diets in Cancer

There currently exist several basic science papers and animal studies pointing to positive effects of ketogenic diets in different types of cancers (24, 34, 35), and this is now moving into human clinical trials. Our current on-going Keto-CARE trial is the world's first and only clinical trial investigating the feasibility and efficacy of a well-formulated ketogenic diet in women with metastatic breast cancer. To date, this trial has demonstrated high levels of tolerance and feasibility as evidenced by mean blood ketones above 0.5mmol, the threshold for nutritional ketosis. Two previous studies also found a high degree of feasibility of the ketogenic diet in human patients with advanced stage cancers (15, 16). Both research teams successfully demonstrated that a ketogenic diet is feasible and well tolerated with no adverse events in advanced stage cancer patients. In a cohort analysis Fine (2012) demonstrated that participants with the highest ketosis levels exhibited either stable disease, or partial remission. While findings were promising, the sample and effect sizes were small, the diets lacked sophistication and were at the lower end of nutritional ketosis, and they were not done in combination with chemotherapy. The patients studied in Fine (2012) were also later stage 4 and thus represented a population that may be more difficult to treat effectively than patients initially diagnosed with BM. A larger study with better control over dietary parameters is needed to determine the response to a ketogenic diet in patients with brain metastases. Despite the sample size limitations, interpretation of the Fine (2012) study reveals that the highest responders to ketosis were most likely to succeed. This finding corroborates results from Schmidt (2011) that showed participants who completed the intervention had higher levels of stable disease or partial remission. There currently exist approximately ten registered clinical trials investigating a ketogenic diet in cancer patients, the majority of which are focused on head, neck, lung and brain primary tumor sites. None of these trials are investigating patients with brain metastasis. Due to the unique etiology and most common tumorigenic pathways, brain metastasis presents a myriad of potential therapeutic mechanisms through which ketosis may target.

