5.0 OBJECTIVES

We propose to conduct a highly controlled feeding study for 16 weeks to examine the effects of an individualized ketogenic or American Institute of Cancer Research (AICR) dietary approach on tumor response to targeted radiation therapy, as well the neural preservation in non-targeted areas of the brain. Our specific aims are as follows:

Primary objective: Assess the feasibility of maintaining a ketogenic versus AICR diet in patients with brain metastasis selected for radiosurgery. Endpoints:

- Circulating glucose (primary endpoint)
- Circulating ketones (primary endpoint)
- Retention
- Side-effects

Secondary objective: Assess the preliminary efficacy of the ketogenic versus AICR diet on tumor response to targeted radiation therapy. Endpoints:

• RECIST v. 1.1 will be utilized to evaluate responses to therapy

Exploratory objective: Assess the preliminary effects of the ketogenic versus AIRC diet on cognitive function and quality of life in BM individuals undergoing radiation therapy.

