Dietary Interventions (16 weeks): Four to seven days prior to the baseline testing, participants in both the Ketogenic and AICR Diet groups will be provided with meals consistent with their diet group that will provide 100% of caloric needs to assist participants with their dietary transition and to ensure participants in the ketogenic arm get into nutritional ketosis by the time of baseline treatment. Food for both diet groups will be provided by a 'ready to eat' meal delivery company along with supplemental snacks. After baseline testing both groups will be provided individualized counseling and support to follow guidelines for each respective eating pattern to maintain their respective diet for the remainder of the study. The Ketogenic Diet will consist of <50 g carbohydrate (personalized based on level of ketones checked daily by finger stick), ~15-20% protein and ~70-75% fat. Total energy intake will be ad libitum to permit overweight/obese participants to restrict caloric intake to induce weight and fat loss for those who are overweight. Participants will be provided with a handheld glucometer (Precision Xtra, Abbott Nutrition) and ketone test strips in order to check the concentration of BOHB from a finger stick. Normal levels of ketones in a person consuming more than 100 grams of carbohydrate per day is <0.1 mmol/L. The goal of the diet will be to induce a state of nutritional ketosis defined as blood ketones >0.5 mmol/L. We believe that a level of ketones above 1.5 mmol/L will enhance the metabolic therapy and deliver better outcomes based on preliminary studies in women with breast cancer (Fine et al., 2012; Schmidt et al., 2011) and blood BOHB concentrations shown to inhibit histone deacetylases (Shimazu et al., 2013b). The carbohydrate level required to induce nutritional ketosis will vary from person to person and thus objective feedback provided by testing blood ketones is a novel tool we will use to personalize the diet by titrating the carbohydrate and protein intake to the participant's individual ketosis threshold. We will encourage consumption of a wide range of ketogenic-appropriate whole foods including non- starchy vegetables, fruits (berries, olives, tomatoes, lemons/limes), meats (beef, chicken, pork, fish, lamb), nuts and seeds, oils (olive, canola, coconut), cheese, butter, cream, and eggs. Contrary to the misconception that the diet is boring or overly restrictive, it is noteworthy that even the most carbohydrate intolerant person can choose from a wide range of whole foods including berries and a wide assortment of vegetables.

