Due to the small sample size proposed (n=24), we will have an enhanced researcher/participant relationship to promote individualized education and counseling to facilitate nutritional ketosis and perceived benefit. We have developed extensive educational materials and resources to help participants successfully make the behavior change to eating a very low-carbohydrate diet and an AICR diet. Well-formulated ketogenic diets are unique when compared to other diets in that there exists an ability to receive direct feedback on participant adherence via finger prick and handheld glucometer that measures the biomarker BOHB. Enrolled participants will be in daily correspondence with research staff throughout the duration of the study to provide a personalized nutrition approach and optimize the amount of time spent in nutritional ketosis and to provide continued support and education for the AICR cohort.

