8.2 Adherence

Participant adherence with the study intervention will be encouraged and monitored in several ways. All participants will be provided a handheld glucometer (Precision Xtra, Abbott Nutrition) and reagent strips that measure BOHB from a small amount of blood obtained by finger stick. Although there is variability between people, BOHB levels in individuals consuming more than 100 grams of carbohydrate per day are usually ≤ 0.1 mmol/L. A primary goal of the initial diet intervention is for each participant to enter nutritional ketosis, which starts at 0.5 mM and extends up to approximately 3.5 mmol/L. This is a strong indication that fat is being used as one's primary fuel, and there may be other therapeutic benefits associated with ketones in this range. Transient increases in ketones above 3.5 mmol/L may occur after exercise, but regulatory feedback systems keep ketones from elevating to dangerous levels that are seen in uncontrolled type-1 diabetics who have insufficient insulin (i.e., >10 mmol/L). Participant's information will be kept private and only made available to IRB approved research staff. During the intervals between research- based visits participants will report their ketone levels daily to the research coordinator and lead RD on the team and adjustments to the diet made accordingly.

We will counsel patients to aim for a level > 1.0 mM while following principles of a well-formulated ketogenic diet. If ketone readings are lower than 0.5 mM, we will individually work with the patient to identify appropriate changes to their diet/lifestyle to achieve nutritional ketosis. The monitoring of daily ketones for patients on the ketogenic diet provides a gold-standard biofeedback marker that is objective and quantifiable for adherence. Deviation from the dietary standards of a well-formulated ketogenic diet will cause rapid decreases in ketones and elevations in blood glucose,

which will be identified in the patient:researcher interaction. For the standard diet arm, this will present a greater challenge. We will ask participants to inform us of dietary deviations and these will be identified and logged. The monthly self-report diaries will be used for tracking any minor adverse effects (GI distress, bloating, gut distension, diarrhea etc.). If participants do not experience any side effects, it is possible they will not have a self-report diary to share monthly.

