9.0 BIOCHEMICAL, COGNITIVE AND PSYCHOSOCIAL TESTING

Activity Monitor:

Physical activity during a course of radiation therapy can be associated with decreased fatigue and may potentially mitigate other side effects. An activity tracker will be worn around the wrist daily for heart rate and step counting.

Peripheral Blood Samples:

Additional lab samples, which are not part of standard care, will be obtained at baseline and paid for as a research cost. Blood will be collected at baseline and every 8 weeks throughout the study duration until terminus.

Continuous Glucose Monitoring (CGM)/ Continuous Ketone Monitoring (CKM):

In order to more accurately quantify the glycemic control and diet adherence of patients using either the AICR or Ketogenic diet we will use three 10-14 day recording periods of CGM/CKM at baseline, midpoint and post-testing. A small Bluetooth compatible unit will be affixed to either the triceps or adipose located near anterior superior iliac spine. CGM/CKM will be analyzed for glucose excursions, mean glucose levels and other markers of glycemic control.

Insulin Resistance and Pre-Diabetes Panels

Due to the high correlation between insulin resistance, diabetes and breast cancer occurrence/prognosis, we will examine the effects of the two diets on several biomarkers including HbA1c, Insulin, Glucose, and Sex hormone binding globulin (SHBG).

Inflammation Panel

Due to the fact that anti-cancer therapies result in increased inflammation, we will examine a panel

of inflammation markers. Each of the following markers is associated with either prognosis or quality of life. The markers to be assessed will be: $TNF-\alpha$ IL-6, IL- 8, CD-14, and CD-16.

Collection and Handling of Specimens

At baseline, and on a monthly basis until study terminus blood will be collected from the participant. Prior to testing all vacutainers will be labeled per study requirements. Blood will be collected into vacutainers, inverted and then stored depending on requirements for each assay.

Cognitive Testing

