17.0 STATISTICAL ANALYSES

Analysis Plan

Unless otherwise specified, all analyses will proceed on an intent-to-treat basis, and hypothesis tests will be two-sided and at the 5% significance level.

The primary objective is to assess the feasibility of maintaining a ketogenic versus AICR diet in patients with brain metastasis selected for radiosurgery. The primary measurements are blood levels of glucose and ketones. Measurements will be taken at baseline, 8 weeks, and 16 weeks. These biomarker outcomes will be analyzed using mixed effects linear regression with fixed effects for timepoint, diet group, their interaction, BMI, and sex. We will use subject-level intercept random effects to account for correlation between repeated measurements within subjects. The primary targets of inference are the treatment effects at each (post-baseline) timepoint. To test the two primary measurements at the two post-baseline timepoints, we will use a 4-way Bonferroni-Holm correction to account for multiplicity. Retention at week 8 and 16, as well as side effects, will be summarized and compared between diet groups.

To assess the preliminary efficacy of ketogenic versus AICR diet on tumor response to targeted radiation therapy, we will use a Chi-squared test for the association between treatment group and partial-or-complete response according to RECIST v1.1.

For the exploratory objective assessing the preliminary effects of the ketogenic versus AICR diet on quality of life in BM individuals undergoing radiation therapy, we will use the same linear mixed effects model as for the primary objective, but with the following quality-of-life endpoints as outcomes: Hearth Hope Index, SF-36, FACT-B, Brief Pain Inventory, and Brief Fatigue Inventory. Tests will be performed without multiplicity correction.

The mixed models used for the primary analyses are applicable to unbalanced data due to chance imbalances, missing data, or drop-out. We will assess the possible impact of non-random missingness using sensitivity analyses.

Power Analysis

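### The primary objective asks whether patients can maintain the diet, but the primary analysis fixes only arm differences in means and never counts patients in ketosis

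*Protocol*

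**What the plan says.** Section 5.0 gives the primary objective: "Assess the feasibility of maintaining a ketogenic versus AICR diet in patients with brain metastasis selected for radiosurgery". Glucose and ketones are its primary endpoints; retention and side effects are listed with them.

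Section 17.0 models glucose and ketones as continuous outcomes in a linear mixed model and states: "The primary targets of inference are the treatment effects at each (post-baseline) timepoint". Two outcomes at two visits give four tests under a Bonferroni-Holm correction. Retention and side effects are summarised and compared between arms outside those four tests. The power analysis is also written in differences of mean change.

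The ketosis level appears elsewhere:
- Dietary Interventions, Section 7: "The goal of the diet will be to induce a state of nutritional ketosis defined as blood ketones >0.5 mmol/L".
- Section 8.2: "A primary goal of the initial diet intervention is for each participant to enter nutritional ketosis, which starts at 0.5 mM". Readings below 0.5 trigger individual dietary work.
- Section 3.2, on the earlier breast cancer trial, cites feasibility "as evidenced by mean blood ketones above 0.5mmol, the threshold for nutritional ketosis".

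Section 9.0 introduces continuous glucose and ketone monitoring partly to quantify adherence, but the analyses it names are these: "CGM/CKM will be analyzed for glucose excursions, mean glucose levels and other markers of glycemic control".

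**The concern.** Whether a diet is maintained is a fact about each patient, and the protocol words its ketosis goal that way. A difference in means answers another question: whether the two diets produced different ketone levels on average. A few patients with high ketones can carry an arm mean while the rest have left ketosis.

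Retention does not fill the gap. A patient at 0.1 mmol/L in week 16 who still attends visits is retained but is not in ketosis.

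What is at stake is the pilot's main product. A larger trial would need to know what share of patients with brain metastases stayed in ketosis through radiosurgery and the following weeks. The analysis as fixed need not give that share, although the data for it are collected.

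**Working it through.** **Inputs from the protocol.** 12 per arm (Section 6.0). Per-test alpha 0.05/4 = 0.0125, the level in the power analysis and the strictest Holm step. SD of ketone change 0.16 mmol and powered difference 0.34 mmol (Power Analysis). Ketones on a non-ketogenic diet about 0.1 mmol/L (Section 8.2). Ketosis above 0.5 mmol/L (Dietary Interventions).

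**Assumptions.** The protocol gives no SD of ketone levels, so the level distributions below are assumed. A two-sample t-test stands in for the mixed model, as in the protocol's own power analysis.

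**1. The plan's own figure.** Noncentrality = 0.34 / (0.16 × √(2/12)) = 5.21. With 22 df and two-sided alpha 0.0125 the power is 98.99%. For glucose, 2.3 / (1.077 × √(2/12)) = 5.23, power 99.05%. The stated 99% reproduces and is not in dispute.

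**2. What the powered difference implies.** Take AICR at 0.1 and, as an assumption, 0.16 as the SD of levels. The ketogenic mean is 0.1 + 0.34 = 0.44. The share above 0.5 is P(Z > (0.5 − 0.44)/0.16) = P(Z > 0.375) ≈ 35%, about 4 of 12. Here the arm mean, below 0.5, would itself show the shortfall.

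**3. Split arm, no spread.** Let k of 12 ketogenic patients sit at one raised level and everyone else at 0.1. Writing q = k/12 and the rise as one unit, the difference is q, the ketogenic-arm variance is 12q(1−q)/11 and the AICR variance is 0. So t = q / √(q(1−q)/11), whatever the raised level is.

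| k | t | pooled p (22 df) | Welch p (11 df) |
|---|---|---|---|
| 4 | 2.35 | 0.028 | 0.039 |
| 5 | 2.80 | 0.010 | 0.017 |
| 6 | 3.32 | 0.003 | 0.007 |

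**4. Split arm, with spread.** Ketotic patients are N(1.0, 0.3) or N(1.5, 0.4), floored at 0.51; all others are N(0.1, 0.05). There were 40,000 simulated trials per setting; ranges run over the two ketotic means. Share significant at 0.0125:

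| Ketogenic patients in ketosis | pooled | Welch |
|---|---|---|
| exactly 6 of 12 | 95%–99% | 66%–80% |
| random count, true rate 50% | 65%–67% | 53%–57% |
| exactly 5 of 12 | 28%–32% | 1%–3% |

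**5. Would the arm mean reveal it?** With six of 12 in ketosis the expected arm mean is (6×1.0 + 6×0.1)/12 = 0.55 or (6×1.5 + 6×0.1)/12 = 0.80, both above 0.5. Significance and an observed arm mean above 0.5 occur together in 79%–99% (pooled) or 57%–80% (Welch) of those trials.

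**6. Precision of the missing estimate.** Exact (Clopper-Pearson) 95% intervals: 6/12 gives 21%–79%; 9/12 gives 43%–95%.

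**The case against.** The strongest reply is that the protocol states nothing false. Ketones are the endpoint, the objective is comparative, and an unseen statistical analysis plan could add a responder summary. Where the protocol itself ties 0.5 to feasibility (Section 3.2) it uses a mean, and the mixed model yields arm means. The goal in Section 8.2 is about entering ketosis, not about a maintenance endpoint.

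Part of this stands. The point is an improvement to a fixed choice, not an error of fact. But the protocol does not leave the primary inference open: it fixes it, and step 5 shows that the arm mean does not stand in for the count.

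The size also depends on the assumptions. The split arm has a within-arm SD of about 0.51–0.78, against the only documented ketone SD of 0.16 (for changes). If levels had SD 0.16 around 0.6–0.7, about 73%–89% of patients would exceed 0.5 and the mean would be informative.

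Several stronger readings are not supported:
- *The protocol treats significance as feasibility.* It nowhere says so.
- *The ketosis level is unused.* It drives counselling; it is absent only from endpoints and analysis.
- *A significant result could hide that nobody was in ketosis.* The test could be significant, but an arm mean below 0.5 would expose this.
- *The levels 0.5, above 1.0 and above 1.5 contradict each other.* The protocol gives them different roles: definition, counselling aim and hypothesised enhancement.
- *Half the arm failing would nearly always give significance.* The 95%–99% is conditional on exactly six of 12 and the pooled test.

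**Conclusion.** The mismatch is real. The objective concerns maintaining the diet, and the only primary inference is a between-arm mean contrast. Followed as written, the plan need not show how many ketogenic-arm patients maintained ketosis. Under the assumed split-arm levels, a significant ketone difference with about half the arm out of ketosis is more likely than not, but it becomes uncommon at five of 12 once spread is allowed for. These rates rest on assumed levels and on a t-test in place of the mixed model; the mismatch itself does not depend on them. This is a cheap improvement. It does not make the planned analysis invalid.

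**What to change.** In Section 17.0, keep the mixed-model contrasts and describe them as evidence that the diets separated. Add, as a feasibility estimate, the proportion of all randomised ketogenic-arm patients with blood ketones above 0.5 mmol/L (the Dietary Interventions definition) at week 8 and at week 16, each with an exact 95% interval. Count missing or withdrawn patients as not maintained, and show deaths and removals for progression (Section 15) separately.

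Two visits are only snapshots, so support the proportion with the share of daily finger-stick readings above 0.5 and the continuous-monitoring time above 0.5. This matches the protocol's own aim to "optimize the amount of time spent in nutritional ketosis". No pass/fail target is needed.

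The cost is a protocol amendment with IRB approval (Section 16.1). No new data are required. The interval will be wide with 12 patients, so the result should be reported as an estimate and not as a test.

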6.0 STUDY DESIGN

This pilot study will be a single center, randomized controlled study of 24 participants with diagnosed BM (various primary disease sites) comparing the effect of a ketogenic (n=12) and AICR (n=12) diet. Randomization will be balanced by blocks of random sizes but no stratification due to the small sample size. Both groups will undergo a 16-week diet intervention. In an effort to maintain a patient centric focus and monitor changes in quality of life (QOL) all patients will complete psychosocial and behavioral inventories. These inventories aim to capture a holistic view on the proposed nutritional intervention during treatment. Primary outcomes will be determined at baseline, 8 weeks, and 16 weeks (see section 13 - Study Calendar) while patient-centric outcomes will be assessed every four weeks.

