8.1 Clinical assessments

Standard of Care Clinic Visits

Participants will be evaluated in the clinic prior to the start of therapy and study intervention, as well as at monthly intervals for history, physical examination for vitals, height, and weight. Hearth Hope Index (HHI), SF-36, cancer specific FACT-surveys, Brief Pain Inventory, and Brief Fatigue Inventory, and self-report diaries (adverse events, adherence and palatability surveys) will be completed to evaluate QOL and will be administered at baseline, monthly during the intervention and at study terminus. Serum or plasma-based biological markers will also be collected at baseline, and midpoint and study terminus. Standard of care brain imaging will be utilized at baseline, 8 and 16 weeks to evaluate disease status and progression. Body composition and bone mineral density will be assessed at baseline and 16 weeks using dual energy x-ray absorptiometry (DXA).

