14 STUDY CALENDAR

	Week				
Tests & observations	0	4	8	12	16
Signed informed consent	Х				
History and Physical Exam	Х				Х
Height/weight	Х	Х	Х	Х	Х

Standard of Care Imaging	Х		X		X
Continuous Glucose/Ketone Monitoring	Х		Х		Х
Ketone Finger Stick	Х	Х	Х	Х	Х
Activity Tracker	Х	Х	Х	Х	Х
DXA Bone & Body Fat Quantification	х				x
Cognitive Testing	Х		Х		X
Review of medications	Х	Х		Х	
Performance status	Х		Х		Х
SF-36	Х			Х	
Brief Pain Inventory Questionnaire (BPI-10)	х		х		х
Brief Fatigue Inventory	Х		Х		Х
FACT Questionnaire	Х		Х		Х
Hearth Hope Index	Х		Х		Х
Blood tests	Х		Х		Х
FFQ questionnaire/3-day food log*	х				

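### The text schedules the quality-of-life inventories every four weeks, but the calendar marks four of them at weeks 0/8/16 and SF-36 at weeks 0 and 12 only; the FACT version analysed is named only in Section 17.0

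*Protocol*

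**What the plan says.** **Schedule in the text.** Protocol Section 6.0 sets the primary outcomes at baseline, 8 and 16 weeks, "while patient-centric outcomes will be assessed every four weeks". Section 8.1 names the Hearth Hope Index, SF-36, the FACT surveys, the Brief Pain Inventory and the Brief Fatigue Inventory, and says that they "will be administered at baseline, monthly during the intervention and at study terminus".

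**Schedule in the calendar.** Section 14 has columns for weeks 0, 4, 8, 12 and 16. The rows for the Hearth Hope Index, FACT, Brief Pain Inventory and Brief Fatigue Inventory are marked at weeks 0, 8 and 16. The SF-36 row has two marks, which read as weeks 0 and 12.

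**Analysis.** Section 17.0 takes as quality-of-life outcomes "Hearth Hope Index, SF-36, FACT-B, Brief Pain Inventory, and Brief Fatigue Inventory" and says "we will use the same linear mixed effects model as for the primary objective". For the primary objective it says "Measurements will be taken at baseline, 8 weeks, and 16 weeks" and "The primary targets of inference are the treatment effects at each (post-baseline) timepoint". It lists no separate visits for the quality-of-life outcomes.

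**Instrument.** FACT-B occurs only in Section 17.0. Section 8.1 refers to "cancer specific FACT-surveys" and the calendar to "FACT Questionnaire"; neither gives a version. Section 9.0 describes the FAACT, an anorexia/cachexia instrument, as the measure of response to starting and keeping the diet. The FAACT is neither in the Section 17.0 outcome list nor named in the calendar.

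**The concern.** The two text sections agree with each other, and the calendar disagrees with both for all five inventories. The protocol gives no order of precedence, so staff working from the calendar and staff working from the text would collect different data.

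For four inventories the calendar only thins the schedule: weeks 4 and 12 go, and weeks 8 and 16 remain. For SF-36 it removes weeks 8 and 16 altogether. A later analysis plan can choose which contrasts to report, but it cannot recover a questionnaire that nobody was asked to complete.

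The FACT question is smaller. The analysis names one version, and the sections that govern collection do not. A reader cannot tell from Sections 8.1, 9.0 and 14 that FACT-B is the form to be given, or whether the FAACT comes on top of it.

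**Working it through.** No sample size, power or alpha figure is at issue. The check sets the schedules side by side and counts forms.

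**Inputs.** 24 participants (Section 6.0); five inventories (Sections 8.1 and 17.0); calendar columns 0/4/8/12/16 (Section 14). Monthly over 16 weeks is read as every four weeks, which agrees with Section 6.0. Full retention is assumed.

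| Inventory | Sections 6.0 and 8.1 | Section 14 |
|---|---|---|
| Hearth Hope Index, FACT, Brief Pain, Brief Fatigue | 0, 4, 8, 12, 16 | 0, 8, 16 |
| SF-36 | 0, 4, 8, 12, 16 | 0, 12 |

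**Total forms**
- Text: 5 inventories × 5 visits × 24 = 600.
- Calendar: 4 × 3 × 24 + 1 × 2 × 24 = 288 + 48 = 336.
- Difference: 600 − 336 = 264.

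**Where the 264 forms fall**
- Four inventories at weeks 4 and 12: 4 × 2 × 24 = 192.
- SF-36 at week 4: 24.
- SF-36 at weeks 8 and 16: 2 × 24 = 48.
- Sum: 192 + 24 + 48 = 264. Only 48/264 = 18% fall on weeks 8 and 16, and all of those are SF-36.

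**How far the SF-36 reading depends on the table layout.** The column positions come from a table extracted from PDF. The row keeps its empty cells (mark, blank, blank, mark, blank), and the neighbouring rows parse cleanly. If the single post-baseline mark belonged to week 4, 8, 12 or 16, SF-36 would have 0, 24, 0 or 24 of the 48 forms at weeks 8 and 16. A shifted mark therefore cannot cover both visits. A mark lost in extraction would escape this bound, so the row should be checked against the source PDF. The conflict in the other four rows does not depend on that check.

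**What the Section 17.0 model can give for SF-36.** The fixed effects are timepoint, diet, their interaction, BMI and sex. A diet contrast at a visit is estimable only if the outcome was observed in both arms at that visit.
- Visits 0 and 12: contrast at week 12 yes; weeks 8 and 16 no.
- Visits 0, 8 and 16: weeks 8 and 16 yes.
- Visits 0, 4, 8, 12 and 16: weeks 8, 12 and 16 (and 4) yes.

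The model still runs on the calendar's SF-36 data. It returns one contrast, at a visit where the calendar marks none of the other four inventories. The protocol's remark that mixed models accommodate missing data does not help, because no participant is scheduled for the form at weeks 8 and 16.

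**FACT.** Version named, by section: 8.1 none; 9.0 FAACT; 14 none; 17.0 FACT-B.

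**The case against.** **The harm is conditional.** SF-36 data are lost only if staff follow the calendar against two text sections that agree. Under the text nothing is lost. This stands and limits the size of the point. It does not remove it, because nothing tells staff to prefer the text.

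**Section 17.0 is not at fault.** A reader might infer that the analysis model is a bad choice or would fail. The documents do not support that. The model targets whatever post-baseline visits exist, and weeks 8 and 16 for quality of life are only an inference from the visits given for the primary objective. The inconsistency is between Sections 6.0 and 8.1 on one side and Section 14 on the other.

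**A count of lost contrasts.** It is tempting to say that the text gives ten diet contrasts at weeks 8 and 16 (five inventories × two visits) and the calendar eight. That count needs the inferred restriction to those two weeks and a single score per inventory, whereas Section 9.0 gives SF-36 eight scored sections. Form counts are the safer measure.

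**FAACT given in place of FACT-B.** A reader might also infer that the wrong form will be administered. That is speculation. FACT-B fits the generic labels in Sections 8.1 and 14, and the FAACT has its own stated purpose in Section 9.0, so it need not be in the Section 17.0 list. What stands is that the collected FACT version is not identified.

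**These endpoints are exploratory.** True: they come from a 24-patient pilot and are tested without multiplicity correction.

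**Conclusion.** The protocol contradicts itself on when the five quality-of-life inventories are given, and the calendar as it reads would leave SF-36 without data at weeks 8 and 16. At full retention the text and calendar differ by 264 forms. The consequential part is the 48 SF-36 forms at weeks 8 and 16: 48 by the text, 0 by the calendar, and at most 24 if its one post-baseline mark has only shifted column. If the calendar is followed, SF-36 yields a week-12 contrast only, out of line with the other four inventories.

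The FACT defect is narrower: the version analysed in Section 17.0 is not identified where collection is described.

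Primary and secondary inference and power are unaffected, and the Hearth Hope Index, Brief Pain Inventory and Brief Fatigue Inventory have weeks 8 and 16 on either schedule. The point is an internal inconsistency that should be corrected because missed questionnaires cannot be recovered. It does not threaten the trial's main conclusions. It rests on full retention for the counts and on the extracted calendar for the SF-36 columns.

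**What to change.** Reconcile Sections 6.0, 8.1 and 14 to one quality-of-life schedule that puts SF-36 at the same visits as the other four inventories, including weeks 8 and 16. There are two ways, neither of which adds a visit, since the calendar already has week 4 and week 12 columns.

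1. **Every four weeks for all five.** For the schedule, only Section 14 changes. Cost: up to 264 more forms than the calendar (192 + 72, the 72 being SF-36 at weeks 4, 8 and 16).
2. **Weeks 0, 8 and 16 for all five.** Total 5 × 3 × 24 = 360 forms, a net 24 more than the calendar (48 SF-36 forms added, 24 dropped at week 12). This gives up weeks 4 and 12 promised in the text, 600 − 360 = 240 forms, and Sections 6.0 and 8.1 must be edited as well as Section 14. It is therefore not the smaller edit, although it is the lighter burden.

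If the 30 minutes in Section 9.0 is taken as the time per session (an assumption), the first option costs 5 × 30 = 150 minutes per participant and the second 3 × 30 = 90. The difference is 60 minutes × 24 = 24 hours over the trial.

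In addition, state in Sections 8.1, 9.0 and 14 which FACT version is collected, so that it matches the Section 17.0 outcome, and say whether the FAACT is additional. The choice of instrument is the sponsor's. This part is wording only.
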